**Table 3: Schedule of Assessments: Phase 2**

Visit/Cycle:	Scrn	Cycle 1					Cycle 2			Cycle 3  – Cycle 12		Cycle 13 and beyond 	EOT 	Follow-up	Follow-up HSCT	Survival Follow-up	
		D -28	D1 	D2	D8	D15	D22	D1 	D2	D15	D1						D15
Informed Consent	X																
Review Entry Criteria	X																
Demographics	X																
Medical and Surgical History	X																
Medication History 	X																
Complete Physical Exam	X												X				
Limited Physical Exam		X		X	X		X			X		X					
Height  and Weight	X	X			X		X			X		X	X				
ECOG PS	X	X			X		X			X		X	X	X	X		
Vital Signs 	X				X		X			X			X			X	
Serial Vital Sign 		X															
Single 12-lead ECG 		Please refer to Table 5															
Serial Triplicate 12-lead ECGs 																	
ECHO/MUGA for LVEF	X									X 			X				
Gene Mutation Analysis 	X																
UGT1A1 Gene Testing	X																
Laboratory Evaluations:																	
Hematology 	X	X		X	X	X	X		X	X	X	X	X			X 	
Serum Chemistry 	X	X		X	X	X	X		X	X	X	X	X			X	
Coagulation Studies 	X	X			X		X			X		X	X			X	
Pregnancy Test 	X	X					X			X		X	X				
Bone Marrow Biopsy and Aspirate 	X						X			X		X	X			X 	

Visit/Cycle:	Scrn	Cycle 1					Cycle 2			Cycle 3  – Cycle 12		Cycle 13 and beyond 	EOT 	Follow-up	Follow-up HSCT	Survival Follow-up
Study Day:	D -28	D1 	D2	D8	D15	D22	D1 	D2	D15	D1	D15	D1		28 Days post Discon	Every 28 Days	Every 28 Days
Peripheral blood for molecular and functional studies of plasma, blasts and neutrophils 	X						X			X		X	X		X 	
Evaluate Extent of Disease and Response to Treatment 							X			X		X	X 		X 	
Transfusion Assessment 	X						X			X		X	X 		X 	
Study Drug Administration 		X	X	X	X	X	X	X	X	X	X	X 				
Compliance Assessment 							X			X		X	X			
PK/PD Assessment 		Please refer to Table 5														
Adverse Events	X	X	X	X	X	X	X	X	X	X	X	X 	X	X 		
Concomitant Medications / Procedures	X	X	X	X	X	X	X	X	X	X	X	X 	X	X	X	
Study Completion 														X	X	X
Survival Status 														X	X	X
New Anti-neoplastic Therapy 														X	X	

D = Day, Discon= discontinuation, EOT=Endo of Treatment, ECG = electrocardiogram, ECHO = echocardiography, ECOG = Eastern Cooperative Oncology Group, HSCT = hematopoietic stem cell transplant, IWG = International Working Group, LVEF = left ventricular ejection fraction, MUGA = multiple gated acquisition, PD = pharmacodynamic, PK = pharmacokinetic, PS = performance status, Scrn = screening

**Note: All cycles are 28 days in duration, there are no rest periods between cycles.**

**Note: Whenever possible, the study visit should occur on the scheduled visit day; a ±2-day window is allowed to accommodate subjects’ schedules.**

- Assessments to be conducted on the last day of study treatment (within 5 days of last dose of study drug).
- All subjects who undergo HSCT following discontinuation of AG-221 are to be followed after the last dose until relapse or end of study. Subjects who relapse and have recurrent IDH2-mutant positive disease may be eligible to restart treatment with AG-221 with Medical Monitor approval; these subjects will ‘re-enter’ the study at Cycle 3 assessments. Subjects who relapse and elect not to restart treatment will enter the survival follow-up phase.
- Subject should be followed (either with In-person visit or contacted by phone) every 28 days to assess for survival status. All subjects are to be followed for survival status follow up every 3 months until death, withdrawal of consent, or end of study for survival.
- Subjects are to remain in the clinic for at least 8 hours after the C1D1 and C2D1 doses for clinical observation, serial triplicate ECGs, serial vital signs (C1D1 only) and PK/PD assessments.

5. To include information on red blood cell (RBC) and platelet transfusions (dates and units administered) and associated hemoglobin levels and/or platelet counts for the 8-week period prior to C1D1.
6. Height is to be obtained only at the screening assessment.
7. Systolic and diastolic blood pressure (BP), heart rate, respiratory rate, and temperature. Assessments should be conducted while the subject is seated or supine.
8. Serial vital signs are to be conducted predose and  $30 \pm 10$  minutes and 2, 4, 6 and 8 hours ( $\pm 15$  minutes) post dose following the morning administration of study drug (prior to performing serial ECG assessments).
9. Refer to [Table 5](#) for complete ECG assessment schedule, including timing of serial samples in Cycles 1 and 2.
10. Procedure is to be conducted on C3D1 and Day 1 every other cycle thereafter (e.g., C5D1, C7D1, etc), at the End of Treatment visit and at the Follow-up visit. The same procedure to evaluate LVEF should be conducted throughout the study.
11. Gene mutation analysis for confirmation of IDH2-mutated disease from a bone marrow sample for subjects in Phase 2 will be based on central laboratory testing performed prior to treatment. A separate tumor (blood and/or bone marrow) sample will be required for central laboratory biomarker analysis (see [Section 10.5](#)). A buccal swab for germ-line mutation analysis will be obtained at screening.
12. Hematocrit, hemoglobin, red blood cell (RBC) count, white blood cell (WBC) count with differential, platelet count, and blast count.
13. If performed, the results and/or samples of hematological assessments, bone marrow biopsies, aspirates, peripheral blood for molecular and functional studies of blasts and neutrophils, and evaluation of the extent of disease and response to treatment will be collected and assessed as part of the study for subjects who undergo HSCT after discontinuation of AG-221. These subjects will be followed at least monthly for assessment of disease response until relapse or end of study.
14. Sodium, potassium, chloride, calcium, magnesium, phosphorus, carbon dioxide (CO2), bicarbonate (HCO3), albumin, total protein, glucose, blood urea nitrogen (BUN), creatinine, uric acid, lactate dehydrogenase (LDH), alkaline phosphatase (ALP), alanine aminotransferase (ALT), aspartate aminotransferase (AST), total bilirubin, direct bilirubin, and indirect bilirubin. In addition, creatine kinase, cardiac troponin, amylase, and lipase are to be obtained at screening, on Day 1 of each treatment cycle, and at the End of Treatment visit.
15. Prothrombin time (PT), activated partial thromboplastin time (aPTT), and international normalized ratio (INR)
16. A serum pregnancy test will be performed at screening (within 7 days prior to first study drug administration) and at the EOT. A urine pregnancy test must be conducted on the day of first study drug administration and confirmed negative prior dosing (Day -3 for subjects undergoing 72-hour PK/PD profile or on C1D1) and Day 1 of all subsequent cycles.
17. Bone marrow aspirates and core sampling should be performed and analyzed at the local site's laboratory in accordance with the International Council for Standardization in Hematology (ICSH) Guidelines ([Lee, et al. 2008](#)) (see [Section 10.7](#)). Investigator assessment of cytogenetic risk group at baseline and results of the bone marrow assessments performed for the evaluation of clinical activity will be collected for an independent review during Phase 2 of the study. Analyses should include cytogenetics and flow cytometry according to institutional standards and results should be recorded in the eCRFs. Studies should be conducted on peripheral blood samples if bone marrow aspirate is not available (e.g., a "dry" tap).
18. Evaluation of disease response, including bone marrow and peripheral blood for plasma and IDH2-mutated cells to be conducted on C2D1, every 28 days during treatment through at least Month 12 (see [Section 10.8.1](#)). Evaluation should be independent of dose delays and/or dose interruptions, and/or at any time when progression of disease is suspected. After at least 12 months, subjects in the Phase 2 portion of the trial, may have the extent of their disease assessed, including bone marrow biopsy, aspirates or peripheral blood based on their response to treatment.
19. Subjects will have the extent of their disease assessed based on modified IWG criteria or other appropriate response criteria for the malignancy under study (see [Section 10.8](#)).
20. Response to treatment is to be assessed at this visit if the subject discontinues treatment for reasons other than disease progression.
21. Subjects are also to be evaluated for RBC and platelet transfusions (dates and units administered) and associated hemoglobin levels and/or platelet counts at each response assessment and as clinically indicated.

- The daily dose on C1D1, C1D2, C2D1, C2D2 and C3D1 are to occur in clinic to accommodate PK/PD sampling (C1D1 and C2D1) or to allow for predose assessments (C1D2, C2D2 and C3D1).
- Treatment compliance is to be assessed based on return of unused drug as well as subject diaries.
- Refer to [Table 5](#) for complete serial PK/PD sampling schedule and to [Section 10.10](#) for details for blood sampling for 2-HG and  $\alpha$ -KG.
- Any serious adverse events (SAEs) that are assessed by the Investigator as possibly or probably related to study treatment that occur >28 days post-treatment also are to be reported.
- Subjects who do not go to HSCT are considered to have completed the study at the time of the Day +28 follow-up assessment; subjects who undergo HSCT after discontinuation of AG-221 remain on study until relapse (or end of study). All subjects enter the survival follow-up phase after study completion.
- After the safety follow-up assessments, or for subjects who relapse after HSCT and elect not to restart treatment, subjects are to be contacted every 28 days to assess survival status until death or end of study. All subjects are to be followed for survival status follow up every 3 months until death or end of study.
-  All new anti-neoplastic therapies administered after the last dose of AG-221 are to be captured for all subjects through end of study.
-  Starting at Cycle 13, all assessments may be reduced to every 3 cycles unless otherwise indicated.
-  Starting at Cycle 13, 3 Cycles of AG-221 should be dispensed.
-  Adverse events and concomitant medication must still be captured every 28 days. On cycle Day 1 (every (28 days) when assessments are not performed documented phone contact is acceptable.

**Table 4: Pharmacokinetic and Pharmacodynamic Sampling and Electrocardiogram Schedule for the Phase 1 Dose Escalation and Part 1 Expansion**

Visit/Cycle:	Scrn	Cycle 1												Cycle 2				Cycle 3				Cycle 4 – Cycle 12				F/U			
Study Day:	D -28	D -3 			D1 			D8		D15			D22		D1		D15		D1		D15		D1			EOT	D +28		
Assessment	Blood/ Urine/ ECG	Blood	Urine	ECG	Blood/ Urine/ ECG	Blood	ECG	Blood	ECG	Blood	Urine	ECG	Blood	ECG	Blood	Urine	ECG	Blood	Urine	ECG	Blood	Urine	ECG	Blood	Urine	ECG	Blood	Urine	ECG
Pre-dose 	X 	X	X	X	X	X	X	X		X	X		X		X	X		X	X		X	X		X	X		X	X	
Post-dose																													
Anytime							X			X		X		X		X				X				X	X	X	X	X	X
0.5 hr		X 		X 		X 		X 					X 											X 					
1 hr		X 						X 					X 											X 					
2 hr		X 		X 		X 		X 					X 											X 					
3 hr		X 						X 					X 											X 					
4 hr		X 		X 		X 		X 					X 											X 					
6 hr		X 		X 		X 		X 					X 											X 					
8 hr		X 		X 		X 		X 					X 											X 					
10 hr		X 	X					X 					X 											X 					
24 hr		X 	X																										
48 hr		X 	X																										
72 hr		X 	X																										

Footnotes continue on next page

D = day; ECG = electrocardiogram, EOT = end of treatment, F/U = follow-up and follow-up post HSCT, Scrn = screening

Notes: For all days with predose samples, subjects should be instructed to take their dose of AG-221 in clinic. All 12-lead ECGs are to be conducted after 3 minutes of recumbency. A 12-lead single ECG should also be obtained as clinically indicated. Serial ECGs (Day -3 or C1D1) should be obtained following vital signs assessments. A subset of samples collected for pharmacokinetic (PK) also will be used to assess cholesterol and 4 $\beta$ -OH-cholesterol levels (Section 10.11).

 Day -3 assessments, including 72-hour PK/PD and serial 12-lead ECGs will be conducted for the first 3 subjects enrolled in each cohort during the dose escalation phase and the first 15 subjects in each arm of Part 1 Expansion following a single dose of AG-221 administered on Day -3; these procedures are optional (based on Medical Monitor evaluation) for any additional subjects enrolled in these cohorts. All screening assessments must be completed prior to single dose administration on Day -3.

 Five urine collections will be obtained during the 72-hour PK/PD sampling time: predose (at least 20 mL) and at the 10-, 24-, 48- and 72-hour blood draws ( $\pm$ 1 hour).

 Only for subjects who did not undergo the Day -3 assessments. Additional urine samples are required during the treatment period for PD assessment (2-hydroxyglutarate [2 HG] and  $\alpha$ -ketoglutarate [ $\alpha$ -KG]).

 To be obtained within 30 minutes before dose; can be done at any time during screening.

 Screening blood sample for analysis of 2-HG and  $\alpha$ -KG only.

 To be obtained within  $\pm$ 10 minutes of specified time.

 Assessments to be conducted on C4D1 only

 To be obtained within  $\pm$ 15 minutes of specified time.

 To be obtained within  $\pm$ 1 hour of specified time.

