In the Phase 2 portion of the trial, eligibility, treatment decisions, and response to treatment will be determined by the Investigators based on modified International Working Group (IWG) response criteria (Table 7 and Table 8). Response will also be assessed retrospectively by an Independent Response Adjudication Committee (IRAC). Subjects in the Phase 2 portion of the trial will have the extent of their disease assessed and recorded at screening, on C2D1, every 28 days thereafter through at least Cycle 12 while on study drug treatment, independent of dose-delays and/or dose interruptions, and/or at any time when progression of disease is suspected. An assessment also will be conducted at the End of Treatment visit for subjects who discontinue the study due to reasons other than disease progression. For those subjects who undergo HSCT following discontinuation of AG-221, disease response assessments are to be conducted at least monthly until relapse or end of study.

Starting at Cycle 13, subjects in Phase 2 in remission may have the extent of their disease assessed every 3 cycles (via bone marrow biopsy, aspirates or peripheral blood) unless the local standard of care (SOC) requires more frequent extent of disease assessments. For those subjects

not in remission, it is reasonable to have the extent of their disease assessed every 1 to 2 months to assess for response.

Subjects in the Phase 2 portion of the trial will also be evaluated for RBC and platelet transfusion requirements, including dates of the transfusion and units administered, as well as the associated hemoglobin levels and/or platelet counts, at each disease response assessment.

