### Phase 2:

An overall objective response rate (ORR, see [Section 12.5.7](#)) of at least 33.6% in 125 subjects (at least 42 responses in 125 subjects) will result in an exact binomial 95% CI with a lower bound greater than 25%, which is clinically meaningful in this setting and exceeds the ORR expected with available therapies ([Roboz, et al. 2014](#)). If 42 responses in 125 subjects are observed (33.6% observed ORR), the 95% CI will be (25.4%, 42.6%). This will be considered as evidence of clinically significant activity of AG-221.

Additional subjects may be needed for the replacement of subjects who are not evaluable for PK/PD, safety, and/or clinical activity, or for evaluation of alternative dosing regimens.

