5. GENERAL STATISTICAL CONSIDERATIONS

5.1. Reporting Conventions

Tabulations will be produced for subject disposition, demographic and baseline disease characteristics, safety, and clinical activity parameters. The study data will be analyzed and reported for efficacy/safety when applicable based on all subjects' data from the Phase 1 dose escalation, the Part 1 Expansion, the combined Phase 1, Phase 2, and the combined Phase 1/2 up to the data cut-off date of 29 July 2019.

Unless specified otherwise, the data will be presented as specified below:

1. In Phase 1 dose escalation, all subjects (combining different malignancy types [overall]) will be utilized. Data will be summarized by total daily dose groups, unless otherwise specified. The total daily dose is defined as the total dose a subject receives during a day based on the assigned or actual dose regimens for efficacy and safety, respectively.
2. In Part 1 Expansion, all subjects (combining different malignancy types) will be utilized and will be grouped into 4 arms (groups):
 - Arm 1: R/R AML and age ≥ 60 years, or any subject with AML regardless of age who has relapsed following a BMT.
 - Arm 2: R/R AML and age < 60 years, excluding subjects with AML who have relapsed following a BMT.
 - Arm 3: Untreated AML and age ≥ 60 years that decline standard of care chemotherapy.
 - Arm 4: IDH2-mutated advanced hematologic malignancies not eligible for Arms 1 to 3.
3. In the combined Phase 1, analyses will be presented by total daily dose groups as < 100 mg, 100 mg and > 100 mg for subjects with R/R AML. The overall subjects in the combined Phase 1 will be summarized by malignancy type including R/R AML, untreated AML, MDS, and other.
4. In Phase 2, data will be summarized primarily for all R/R AML subjects.
5. In the combined Phase 1/2, R/R AML will be presented by total daily dose groups as < 100 mg, 100 mg and > 100 mg, and the overall subjects will be presented by malignancy type.

For subjects who were discontinued from study treatment, underwent HSCT, and then re-started AG-221, data after restarting AG-221 will be excluded from all summary analyses except for death. The data collected after restarting AG-221 will be provided in listings.

Categorical variables will be summarized by frequency distributions (number and percentages of subjects) and continuous variables will be summarized by descriptive statistics (number of subjects, mean, standard deviation (SD), median, minimum, and maximum).

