10.2. Analysis of Primary Efficacy Endpoint

The primary efficacy endpoint of ORR is defined as the rate of responses including CR, CRi, CRp, PR, mCR (for MDS) and MLFS (for AML) by investigator assessment. The ORR will be summarized by the percentage of responses primarily in the FAS with 2-sided exact binomial 95% CI.

Response will also be summarized by the best objective response following the hierarchical order of CR, CRi/CRp, PR, mCR/MLFS, stable disease, relapse/progressive disease/failure, and not evaluable (NE).

An observed ORR in the pivotal Phase 2 R/R AML FAS subjects with the lower bound of the exact binomial 95% CI greater than 25% is deemed clinically meaningful and exceeds the expected ORR with other available therapies. This will be considered as evidence of clinically significant activity of AG-221. The analyses in the combined Phase 1/2 R/R AML on total daily dose of 100mg utilize larger population and thus provide robust estimate of ORR to better describe the clinical activity of AG-221.

To assess the robustness of the primary analysis, the following sensitivity analyses will be performed:

- (1) ORR in the EAS for the combined Phase 1, Phase 2, and the combined Phase 1/2;

- (2) The ORR assessed by Independent Response Adjudication Committee (IRAC) in the FAS for Phase 1, Phase 2, and the combined Phase 1/2 R/R AML.

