10.3.1. Key Secondary Efficacy Endpoints

10.3.1.1. Complete Response Rate

CRR is defined as the rate of CR according to modified IWG response criteria.

Number and percentage of subjects with CR and the 2-sided exact binomial 95% CI for CRR will be summarized for Phase 1 dose escalation, Part 1 Expansion, the combined Phase 1, Phase 2, and the combined Phase 1/2 for the FAS as described in items 1 to 5 of [Section 5.1](#).

The following sensitivity analyses will be performed for Phase 1, Phase 2, and the combined Phase 1/2 :

- (1) CRR in the EAS;
- (2) CRR assessed by IRAC in the FAS.

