10.3.1.4. Duration of Response

Among subjects who have a response of CR, CRi, CRp, PR, or mCR/MLFS by investigator assessment, DOR will be calculated as the date of the first documented response to the date of the first documented disease relapse, progression or death due to any cause, whichever occurs first. Subjects without relapse, progressive disease, or death due to any cause will be censored at the date of the last adequate response assessment.

Table 3: Censoring Rules for Duration of Response

End Date for Duration of Response	Censored (Y,N)	Scenarios
The earliest of death date, relapse date, and progression date	N	A subject has less than 2 consecutive missing response assessments prior to a documented death, relapse, or progression which is before any subsequent anti-cancer therapy.
The last adequate response assessment date before missing assessments	Y	A subject has 2 or more consecutive missing response assessments prior to a documented death, relapse, or progression.
The last adequate assessment date	Y	If a subject did not die, did not relapse or progression, and did not receive any subsequent anti-cancer therapy.
The last adequate assessment date on or prior to the start of subsequent anti-cancer therapy	Y	If a subject did not die, did not relapse or progression on or prior to subsequent anti-cancer therapy.
The last adequate assessment date on or prior to the start of subsequent AML therapy	Y	If a subject died, relapsed, or had disease progression after receiving subsequent anti-cancer therapy.
1) If response assessment after a single documented progressive disease /relapse shows response including CR, CRi, CRp, PR, mCR/MLFS, the relapse/progression before documented response is considered as NE. 2) Subsequent anti-cancer therapy in this table excludes HSCT.		

DOR will be summarized primarily based on investigator assessment. The DOR will be analyzed using KM methods and KM curves. The 25th percentile, median and 75th percentile of the response duration with 2-sided 95% CI will be provided for overall responders in the FAS for Part 1 Expansion, the combined Phase 1, Phase 2, and the combined Phase 1/2 as described in items 2 to 5 of [Section 5.1](#). KM estimates at 3, 6, 9 and 12 months will be provided at individual time points. Due to the limited sample size of each total daily dose group, DOR will not be analyzed for Phase 1 dose escalation.

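### CRR has no cut-off at transplant, so a CR first seen after HSCT conditioning counts as an AG-221 complete response

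*Protocol*

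**What the plan says.** **Data collected after HSCT.** Footnote 13 of Protocol Table 3 covers subjects transplanted after stopping AG-221. Where assessments are performed, "evaluation of the extent of disease and response to treatment will be collected and assessed as part of the study". Protocol 10.8.2 goes further for Phase 2: "disease response assessments are to be conducted at least monthly until relapse or end of study".

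**Definition of the rates.** SAP 10.2: "Response will also be summarized by the best objective response following the hierarchical order of" CR, CRi/CRp, PR, mCR/MLFS and so on. SAP 10.3.1.1: "CRR is defined as the rate of CR according to modified IWG response criteria". SAP 10.3.1.2 and 10.3.1.3 define CR/CRh and CR/CRi/CRp as the share of subjects with that best response. None of these sections names a last eligible assessment. The only general limit is the data cut-off of 29 July 2019 in SAP 5.1.

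**What is set aside.** For subjects who restart drug after transplant, SAP 5.1 states that "data after restarting AG-221 will be excluded from all summary analyses except for death". Protocol 12.3 lists and analyses separately any response assessment made after documented progression.

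**HSCT in the time-to-event analyses.** SAP Table 3, footnote 2: "Subsequent anti-cancer therapy in this table excludes HSCT". Protocol 12.5.7 plans sensitivity analyses with censoring at transplant for duration, time to response/remission and EFS. The SAP plans HSCT censoring as a sensitivity analysis for DOR and OS. Its time-to-response sections (10.3.2.4 to 10.3.2.7) contain no such analysis, and SAP Section 13 does not list its removal as a change from the protocol.

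**The concern.** CRR is a key secondary endpoint in a Phase 2 portion that Protocol 12.5.7 calls pivotal. It is meant to describe remissions obtained with AG-221. The protocol itself describes conditioning and induction-type regimens used for HSCT as anti-neoplastic (Sections 7.1.4 and 9.9.1). A subject may proceed to HSCT after an adequate response, a term the protocol does not define, so transplant in PR, MLFS, CRi or CRp is possible. If the marrow and counts first meet CR criteria after conditioning, a plain best-response derivation credits that CR to the drug. The AML criteria require no minimum duration of CR, so one assessment is enough.

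Three results are exposed: CRR rises, time to CR takes a post-transplant date, and the subject enters DOCR with a duration made up entirely of post-transplant time. The sensitivity analyses planned for CRR (EAS and IRAC) do not remove such a case. The EAS excludes concomitant treatment for the malignancy but does not name later HSCT, and SAP 15.3 gives the IRAC no cut-off.

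**Working it through.** **1. The plan's own figure.** Protocol 12.1 gives 42/125 = 33.6% with exact 95% CI 25.4% to 42.6%. Clopper-Pearson gives 25.40% to 42.60%, so it is reproduced. At 41/125 the lower bound is 24.67%, so 42 is the minimum for the ORR rule. The documents set no target for CRR, CR/CRh or CR/CRi/CRp.

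**2. Is a post-HSCT assessment inside the window?**
- Collected as study response data: yes (Protocol Table 3 footnote 13; Protocol 10.8.2).
- Removed by SAP 5.1: only if AG-221 was restarted. Data between HSCT and restart stay in.
- Removed by Protocol 12.3: only after documented progression.
- Removed by the SAP 10.2 or 10.3.1.1 definitions: no.
- Protocol 12.5.7 censors time to response/remission at transplant as a sensitivity analysis only. That serves a purpose only if the main analysis can count a remission first seen after transplant.

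By contrast, SAP 10.3.1.6 limits transfusion independence to the treatment exposure period, so a window was written where one was intended.

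**3. Which rate moves when CR is first seen after HSCT?** Change in number of responders per subject:

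| Best response before HSCT | ORR | CRR | CR/CRi/CRp | CR/CRh |
|---|---|---|---|---|
| CRi or CRp, CRh already met | 0 | +1 | 0 | 0 |
| CRi or CRp, CRh not met | 0 | +1 | 0 | +1 |
| PR or MLFS | 0 | +1 | +1 | +1 unless CRh already met |
| No response | +1 | +1 | +1 | +1 |

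**4. Size.** Each subject adds 1/125 = 0.8 percentage points. For b on-drug CRs and k CRs first seen after HSCT, CRR = (b + k)/125. Neither b nor k is in the documents; the values below are assumptions for illustration.

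| On-drug CRs (b) | k = 0 | k = 1 | k = 5 | k = 12 |
|---|---|---|---|---|
| 19 | 15.2% | 16.0% | 19.2% | 24.8% |
| 25 | 20.0% (13.4 to 28.1) | 20.8% (14.1 to 29.0) | 24.0% (16.8 to 32.5) | 29.6% (21.8 to 38.4) |
| 31 | 24.8% | 25.6% | 28.8% | 34.4% |

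Parentheses give exact 95% CIs.

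**5. DOCR.** SAP 10.3.2.2 starts the clock at first documented CR and uses censoring similar to SAP Table 3, where HSCT is not subsequent therapy. A CR first seen after HSCT therefore starts a duration that is not cut at HSCT. The protocol's sensitivity analysis cannot repair it, because censoring at transplant would fall before the start date.

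**The case against.** No sentence in either document says that a post-HSCT CR is credited to AG-221. Footnote 13 is about data collection, and the stated purpose of follow-up after HSCT is outcome until relapse or end of study, which reads as durability follow-up. In Protocol 12.5.7 the wording that carries transplanted subjects along appears under DOR, DOCR and EFS, not under ORR, CRR, TTR or TTCR. The authors may have meant only durations to cross the transplant. This stands as a statement of possible intent, but it is not a rule a programmer can apply, and the planned sensitivity analysis for time to response/remission points the other way.

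A reader might take SAP Table 3, footnote 2, as proof that post-HSCT remissions count. It does not go that far: it is confined to that table and governs duration censoring.

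A reader might also infer that the window is equally open after other anti-leukemic therapy. Support is weak. In the Phase 2 schedule, response evaluation stops at end of treatment except in HSCT follow-up, although Protocol 7.1.4 and 8.5 mention following disease status.

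Two further points stand. Transplant dates are listed by subject and post-treatment therapies are linked for subject-level review (SAP 8.4.3), so affected cases could be found. And a deepening drug response cannot be excluded for every subject whose CR is first recorded after HSCT. Neither point produces a CRR free of the problem. For CR/CRh, which rests on the IRAC, a committee charter might set a window; none is in these documents.

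**Conclusion.** The point holds for CRR as the SAP is written. The window is open at HSCT, the resulting bias can only be upward, and no planned sensitivity analysis of CRR removes it. DOCR and time to CR follow the same dates. CR/CRi/CRp is affected only if the pre-HSCT response was PR, MLFS or none, and CR/CRh only if CRh had not already been met.

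The size is unknown. It is 0.8 points per subject at N=125, and the number of such subjects could be zero. Any total depends on a transplant rate, a share below CR at transplant and a CR rate afterwards, none of which the documents give.

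A reader might infer that the pivotal claim is at risk. The documents do not support that. The only success rule concerns ORR, with the "lower bound of the exact binomial 95% CI greater than 25% is deemed clinically meaningful", and a subject who already responded stays a responder. The residual exposure is a non-responder sent to HSCT, possible because an adequate response is undefined; it would matter only at the margin, where 42 against 41 responders decides the bound.

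**What to change.** In SAP 10.2 and 10.3.1, state that best response and the CR, CR/CRh and CR/CRi/CRp rates, by investigator and by IRAC, are derived from assessments before the start of HSCT conditioning or HSCT. Extend the cut-off to other subsequent anti-leukemic therapy if any response data exist after it. Date DOCR and time to CR from the same assessments. Show the rates including later assessments as supportive, so that results remain comparable with the 2016 and 2017 data cuts in SAP Section 12. Keep the planned post-HSCT follow-up of relapse and death for DOR.

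The cost is a short SAP addition, a date filter on transplant and new-therapy dates that are already collected, and one extra table. CRR may come out slightly less favourable.
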